10.7 Deviations to the Study Protocol

All protocol deviations will be identified, recorded and presented in a protocol deviation log. Additionally, any major protocol deviations which increase Subject risk or impact clinical study endpoints will be identified and subsequently tabulated in summary tables. These may include but are not limited to improper consent of Subject, failure of Subject to meet all inclusion criteria and none of the exclusion criteria prior to randomization, and Subject noncompliance.

Any departure or deviation from the originally planned statistical methodologies will be documented and discussed in the SAP, which will include the statistical rationale for diverting from the originally planned statistical summaries and/or analyses.

10.8 Interim Data Review

There is no formal planned interim analysis for this clinical study. However, there is one planned interim data review with one planned final data analysis. Planned interim data review will be conducted when approximately 60 subjects have completed Visit 9 or completed the study. Data from this interim data review will be used to verify the assumptions for sample size calculation or to re-estimate the sample size (Section 10.1). The interim analysis will be based off of the ITT subject population of available data.

10.9 Handling of Missing or Spurious Data

There will not be a specific algorithm for imputing missing data for this clinical study. All recorded data will be used in the analysis of pertinent endpoints and will be presented in the subject data listings as well.

11 Receiving, Storage, Dispensing and Return of Study Products

11.1 Shipment and Receipt

KCI will ensure that no study product will be released to a site until KCI receives written confirmation that the IRB has approved the study at that site.

Prior to the release of study product to the sites, KCI will complete the appropriate accountability forms, which will accompany the shipment of the study product and serve as a shipping record from KCI.

Upon receipt of product, the Investigator, or designee, will inventory the shipment and verify the lot numbers (Customizable kits) and serial numbers (ActiV.A.C. units) against the information provided on the accountability forms. The Investigator, or designee, will sign the form(s) and return it to the KCI monitor, or designee, with notations regarding any missing study product or other discrepancies.

11.2 Study Product Storage

The Customizable kit (Customizable dressing and other materials) and ActiV.A.C. units, are to be stored in a dry location at controlled room temperature away from direct sun exposure in a secure, limited access area under the control of the Investigator.

If storage issues are identified, the site will insure that conditions be brought into compliance. The deviation should be relayed to KCI and the governing IRB as applicable to local or central IRB policies. Situational guidance and corrective means will be assessed and provided by KCI as appropriate.

At the time of the initial site training for the clinical investigation, the KCI monitor will verify that the study products are stored in a secure, limited-access location.

11.3 Study Product Accountability

Each site will inventory and account for study product used throughout the course of the study utilizing accountability forms provided by KCI.

All study products and study-related supplies must be accounted for whether used or unused. The KCI monitor will verify that study product documentation is maintained in the appropriate Subject or study files during monitoring visits. If there is an urgent need to replace any missing or otherwise discrepant shipment contents, the Investigator, or designee, will contact the KCI monitor, or designee, immediately.

ActiV.A.C. units will be returned to KCI after use by a Subject. Each site has authorization from KCI to destroy dispensed Customizable dressings on site per their local biohazard policy.

In the event a malfunction or an adverse device-related event occurs with a dispensed ActiV.A.C. unit, the device will be returned to KCI USA, Inc. as expeditiously as possible.

At the completion of the study, there will be a final reconciliation of study product shipped, used, and returned. Undispensed ActiV.A.C. units and Customizable kits will be returned to KCI.

12 Data Handling and Record Keeping

12.1 Investigator/Site Staff Training

The Investigator and site staff will be trained on the study as a whole, use of the study products, and any specialized procedures prior to and/or during the site initiation visit. KCI will provide clinical support to site staff for any questions or concerns related to study products and treatments; however, KCI will not have influence on Subject care.

12.2 Electronic Case Report Form and Source Documents

Source documents include all information in original records, certified copies of original records, of clinical findings, observations, or other activities necessary for the reconstruction and evaluation of the study. All source documents should be completed in their entirety in a neat, legible manner to ensure accurate interpretation of the data.

Data from source documents of each Subject will be entered into the Subject's electronic Case Report Form (eCRF). Guidance for eCRF completion will be provided and reviewed with the site staff before the start of the study.

12.3 KCI USA, Inc. Monitoring of Study Data

The Investigator will allow access to his/her clinical study records for periodic on-site monitoring visits by a KCI representative, with the understanding that the representative is bound by professional secrecy and will not disclose a Subject's personal identity or personal medical information. The KCI representative will review eCRFs for completeness during on-site monitoring visits and after the eCRFs are submitted to KCI; any discrepancies will be resolved with the Investigator or designee, as appropriate. The data will be entered into the clinical study database and verified for accuracy.

12.4 Data Handling

KCI is responsible for compilation and verification of the clinical study data, retention of the clinical study database, performance of statistical analysis, and preparation of the data reports.

12.5 Records Retention

The Investigator will maintain all study documentation in his/her possession and/or control and institute measures to prevent accidental or premature destruction of any data and/or documents related to the study.

After formal discontinuation or completion of the study, the Investigator will retain all clinical study documentation produced by the Investigator and/or designee(s) for a minimum of three (3) years or in accordance with the regulations in effect for the jurisdiction where the site is located.

13 Administrative Requirements

13.1 Good Clinical Practice

This study is to be conducted according to US and international standards of good clinical practice (FDA Title 21 part 312 and International Conference on Harmonisation guidelines), applicable government regulations and institutional research policies and procedures.

13.2 Ethical Considerations

This protocol and any amendments will be submitted to a properly constituted IRB in agreement with local laws, for formal approval of the study. The decision of the IRB concerning the conduct of the study will be made in writing to the Investigator and a copy of the decision will be provided to KCI before initiation of the study at the site. The Investigator will provide a list of IRB members and their affiliates to KCI.

13.3 Subject informed Consent

Written informed consent will be obtained from a potential Subject after the study has been fully explained and prior to the conduct of any study-related procedures. Obtaining informed consent is a process that must be documented in compliance with GCP, IRB and other applicable regulatory requirements. The Investigator is responsible for continuing an open conversation with the Subject in regard to their continued participation in the study.

13.4 Confidentiality

Information collected about Subjects during the study will be kept confidential and managed according to the requirements of the Health Insurance Portability and Accountability Act of 1996 (HIPAA). This law requires signed Subject authorization informing the Subject of the following:

- What protected health information (PHI) will be collected from Subjects in this study
- Who will have access to that information and why
- Who will use or disclose the information
- The rights of a Subject to revoke authorization for use of their PHI

In the event that a Subject revokes authorization to collect or use PHI, the Investigator retains the ability to use all information collected prior to the revocation of Subject authorization. For Subjects who have revoked authorization to collect or use PHI, attempts should be made to obtain permission to collect at least vital status (i.e. that the subject is alive) at the end of their scheduled study period. *Clinicaltrials.gov Registration*

A description of this study will be available on <http://www.ClinicalTrials.gov> as required by U.S. law. This website will not include information that identifies Subjects. At most, the website will include a summary of the results of the study and will be available for public review at any time.

12. QUALITY CONTROL/QUALITY ASSURANCE14

LIST OF ABBREVIATIONS AND DEFINITIONS

AE	Adverse Event
CI	Confidence Interval
CRF	Case Report Form
CRI	Clinically Relevant Interventions
Customizable™	Prevena™ / Prevena Plus™ Customizable™ dressing with ActiV.A.C
DOS	Day of Surgery
FAS	Full Analysis Set Population
ITT	Intent-To-Treat Population
MedDRA	Medical Dictionary for Regulatory Activities
POD	Post Operative Day
SAP	Statistical Analysis Plan
SOC	Standard of Care
SOP	Standard Operating Procedure
SP	Safety Population
SSC	Surgical Site Complications
SSI	Surgical Site Infection
TEAE	Treatment-Emergent Adverse Event

1. PURPOSE

The purpose of this abbreviated statistical analysis plan (SAP) for the AHS.2012.Customizable.01 study is to outline the analyses planned to support the completion of the Clinical Study Report (CSR) based on the requirements and guidelines identified by the U.S. Food and Drug Administration (FDA). This document is a supplement to the clinical protocol, which should be referred to for details regarding the study objective, design and endpoints.

2. OVERVIEW OF STUDY DESIGN

This is a post-market, open-label, prospective, randomized controlled study to evaluate the safety and effectiveness of Customizable™ when used to manage extensive vertical, transverse, and fleur-de-lis surgical incisions resulting from the primary closure of incisional hernia repair and/or functional panniculectomy procedures. Study data are analyzed for clinical outcomes through 34 days.

At the time of the interim data review, approximately 60 subjects will have been enrolled at two clinical sites in North America. Each subject will be randomized in a 1:1 ratio, stratified by clinical site and type of incision (fleur-de-lis vs. transverse/vertical), to receive either Prevena™ Customizable™ dressing/Prevena Plus™ Customizable™ dressing with ActiV.A.C (Customizable™) or Standard of Care (SOC). Subjects assigned to treatment with Customizable™ will receive treatment for five to seven days post surgery prior to removal of the treatment. Subjects in the SOC arm will receive treatment with standard of care surgical incision dressing one to three days prior to the removal of the treatment. Subjects will be assessed for surgical site complications (SSC) and clinically relevant interventions (CRI) at treatment removal and at Day 10, Day 14, Day 21 and Day 30 post-surgery visits. Subjects will also be assessed for any SSC and any CRI at any unscheduled visit.

The following table provides a general depiction of the study visit/period schedule.

Study Visit/Period	Study Day		
Screening Visit	0 - 45 days prior to surgery		
Surgery/ Randomization/ Treatment Application	Panniculectomy or Incisional Hernia Repair followed by randomization to Prevena™ Customizable™ dressing/Prevena Plus™ Customizable™ dressing with ActiV.A.C (Customizable™) or Standard of Care dressing (SOC).		
Treatment Period	
 
 Customizable™ 5-7 Days	SOC 1-3 days	
 
	Customizable™ 5-7 Days	SOC 1-3 days
Customizable™ 5-7 Days	SOC 1-3 days		
Follow-up Period	Follow-up visits at Days 10, 14, 21, and 30 and unscheduled visits.		

3. STUDY OBJECTIVE

The primary objective of the study is to compare surgical incision-related clinical outcomes in subjects undergoing abdominal surgery for incisional hernia repair and/or functional panniculectomy when managed with Customizable™ as compared to standard of care surgical incision dressing (dry sterile dressing/gauze, steri-strips).

4. EVALUATION CRITERIA

4.1 Primary Endpoint

The primary endpoint for this study is the subject incidence of surgical site complication (SSC) with Customizable™ as compared to the SOC treatment group. SSC is defined as one of the following:

- Dehiscence
- Surgical site infection (SSI)
 - Superficial SSI
 - Deep SSI

4.2 Secondary Endpoint

The secondary endpoint for this study is the subject incidence of clinically relevant interventions (CRI) of the surgical incision in Subjects managed with Customizable™ as compared to the control group managed with a SOC surgical incision dressing. For this study, clinically relevant interventions are defined as the following:

- Antimicrobial treatment of SSI
- Percutaneous and open drainage of the surgical incision (by surgeon)
- Debridement of the surgical incision
- Re-operation related to the surgical incision
- NPWT applied to the open surgical incision

No analysis for the secondary endpoint will be performed due to the early termination of the study.

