3.3 Secondary Study Endpoint

3.3.1 Clinically Relevant Interventions

Incidence of clinically relevant interventions (CRI) of the surgical incision in Subjects managed with Customizable as compared to the control group managed with a SOC surgical incision dressing. For this study, clinically relevant interventions are defined as the following:

- Antimicrobial treatment of SSI
- Percutaneous and open drainage of the surgical incision (by surgeon)
- Debridement of the surgical incision
- Re-operation related to the surgical incision
- NPWT applied to the open surgical incision

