5.7.2 Clinically Relevant Interventions (CRI)

If a SSC requires intervention, the procedure must be documented. Any subsequent CRI for a SSC that resolves and then recurs will be documented as a separate CRI.

5.7.2.1 Antimicrobial treatment of SSI: administration of antibiotics, antifungals, or other antimicrobials for the treatment of an infection related to the surgical incision.

5.7.2.2 Percutaneous or Open Drainage (by surgeon): decompression of the fluid accumulation using either:

1) Percutaneous drainage of incisional fluid;

- OR -

2) Open technique (at bedside) drainage of incisional fluid;

- OR -

3) Open surgical intervention (in a procedure room or operating room) drainage of incisional fluid.

If infection is suspected, Customizable should be discontinued, cultures should be obtained, and clinically significant results documented as an adverse event.

5.7.2.3 Debridement: Removal of necrotic, damaged, or infected wound tissue either at the bedside or in the operating room. Debridement involving muscular fascia or deeper tissues should be documented as reoperations.

5.7.2.4 Reoperation: Procedure requiring dissection deeper than the skin and subcutaneous tissue, repair of the muscular fascia, entry into the retro-peritoneum, renal transplant revision or graft removal, flaps, and skin graft procedures.

5.7.2.5 NPWT: Application of NPWT for management of the opened surgical incision (wound).

[figure not shown]

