5. GENERAL STATISTICAL CONSIDERATIONS

5.1 Scope of Abbreviated Analysis

All analyses described in this abbreviated SAP will be based on the available data for all enrolled subjects. The scope of analyses will include:

- General Analysis: Enrollment, disposition, informed consent, baseline demographics and characteristics.
- Analysis for primary endpoint – Primary effectiveness analysis.
- Analysis of safety measures.

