5.2 Sample Size and Power

Per the protocol, at the time of the trial design,

“A 35% rate of SSC is projected for the SOC arm, which is consistent with the clinical experience of the Investigators. Based on the primary endpoint of incidence rate of SSC, Fisher’s exact test with a two-sided significance level $\alpha = 0.05$ will have approximately 80% power to detect the difference between an incidence rate of 35% in the SOC arm and an incidence rate of 8.75% in the Customizable arm (a 75% reduction) when the sample size in each arm is 44. To account for possible Subject replacement, the sample will be increased by up to 15% for a maximum total of 102 Subjects (51 in each treatment arm).”

The study was terminated early before it reached the final planned sample size of 102 subjects. The study enrollment was stopped on Friday, June 30, 2017. The decision of early termination was made after the interim data review described in Section 10 of this document. A total of 71 subjects (36 in Customizable™, 35 in SOC) were enrolled in this study.

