5.3 Analysis Populations

The following subject populations for this clinical study are:

Safety Population – The Safety population will consist of all subjects who are randomized and do not withdraw before the attempt to apply the assigned treatment with Customizable™ or SOC surgical incision dressing regardless of its duration. Subject data will be analyzed in the arm to which they were treated. All safety results for this study will be presented based on the safety population.

Intent-to-Treat (ITT) Population – The ITT population will consist of all subjects who are randomized and do not withdraw before the attempt to apply the assigned treatment with Customizable™ or SOC surgical incision dressing regardless of its duration. Subject data will be analyzed in the arm to which they were randomized. All supportive or exploratory analyses for this study will be presented based on the ITT population.

Full Analysis Population (FAS): The FAS subject population will consist of all subjects who i) met all of the pre-operative and intra-operative inclusion criteria and none of the pre-operative and intra-operative exclusion criteria, ii) have been randomized, and iii) received treatment with either Customizable™ or SOC dressing. Subjects without SSC will need to receive at least 5 days of Customizable™ or at least 1 day of SOC dressing to be included in this set and completed Day 30 (\pm 4 days). Subjects with SSC prior to Day 30 (\pm 4 days) will be included in this set regardless of length of Customizable™ or SOC dressing treatment and treatment follow up. Subject data will be analyzed in the arm to which they were randomized and treated. The primary and secondary effectiveness analyses for this study will be based on the FAS population.

Subjects having important disqualifying protocol deviations will be excluded from ITT and/or FAS based on the results from the protocol deviation review described in Section 5.4 of this document.

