9. DESCRIPTION OF OTHER PLANNED ANALYSES

No other planned analyses will be performed.

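### SAP 4.2 cancels all analysis of the only secondary endpoint (CRI) because of early termination, although the protocol already has a fallback for sparse data; SAP 7.1 also omits the promised 95% CI for the SSC difference

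*SAP*

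**What the plan says.** Protocol 3.3.1 names one secondary endpoint: "Incidence of clinically relevant interventions (CRI) of the surgical incision in Subjects managed with Customizable as compared to the control group". SAP 4.2 repeats it as subject incidence. On collection, SAP 2 states: "Subjects will be assessed for surgical site complications (SSC) and clinically relevant interventions (CRI) at treatment removal", and continues with the Day 10, 14, 21 and 30 visits and any unscheduled visit.

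Protocol 10.5.2.1 plans a zero-inflated Poisson or negative binomial (ZIP/ZINB) model for the number of CRI. If the number in one arm is inadequate for that model, it substitutes subject incidence by arm, Fisher's exact test at two-sided 0.05 and a 95% CI for the difference. It also plans a supportive incidence comparison on ITT and FAS.

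SAP 4.2 ends: "No analysis for the secondary endpoint will be performed due to the early termination of the study". The effectiveness item in the scope list of SAP 5.1 reads "Analysis for primary endpoint – Primary effectiveness analysis", and SAP 9 adds "No other planned analyses will be performed". SAP 5.3 nevertheless keeps the sentence "The primary and secondary effectiveness analyses for this study will be based on the FAS population".

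On timing, SAP 5.2 says: "The decision of early termination was made after the interim data review described in Section 10 of this document". SAP 10 prints the by-arm SSC rates from that review: 17.2% of 29 on Customizable and 3.1% of 32 on SOC.

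For the primary endpoint, protocol 10.5.1 promises a 95% CI for the SSC rate difference. SAP 7.1 gives rates, components and Fisher's test at 0.048, but no interval. Protocol 10.7 says the SAP will give the statistical rationale for departures from planned analyses.

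**The concern.** The only reason given for dropping CRI is an event that also befell the primary endpoint, which is kept. CRI was scheduled at the same visits as SSC, and the protocol foresaw too few events and wrote a simple analysis for that case. The SAP cancels the fallback along with the model and does not say why a two-row table cannot be produced.

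Two things are at stake. A planned endpoint was removed in a document that already contains the by-arm SSC result, and a reader of the report will have no CRI comparison against which to judge that choice. Separately, in a trial stopped at 71 of 102 subjects, an interval is the natural way to show which effects the data rule out, and the SAP no longer plans one.

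**Working it through.** **1. The design figure.** Inputs from protocol 10.1: 35% v 8.75%, 44 per arm, Fisher's exact test, two-sided 0.05. Power is the sum of Bin(i; 44, 0.35) × Bin(j; 44, 0.0875) over all tables (i, j) with Fisher p ≤ 0.05. Result: 80.7%, against about 80% stated. Inflation: 44 × 1.15 = 50.6, so 51 per arm and 102 in total, as stated.

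**2. What truncation costs the primary test.** The same calculation at the enrolled 36 v 35 (SAP 5.2) gives 77.3%, at alpha 0.05 and at 0.048. At the interim FAS sizes, 29 v 32 (SAP 10), it gives 68.3% at 0.05. The final FAS size is not stated. The loss is real, but the SAP still considers the primary test worth doing.

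**3. CRI passages side by side.**

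| Place | Position on CRI analysis |
|---|---|
| Protocol 10.5.2.1 | ZIP/ZINB; if counts inadequate, incidence + Fisher + 95% CI |
| SAP 4.2 | none |
| SAP 5.1 | not in scope |
| SAP 5.3 | secondary analysis assigned to the FAS |
| SAP 9 | nothing further |

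Too few events would explain not fitting the count model. It does not explain dropping the incidence comparison, which the protocol wrote for that situation.

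**4. The missing SSC interval, illustrated on interim data.** Counts implied by SAP 10: 5/29 = 17.2% and 1/32 = 3.1%.

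- Difference (Customizable minus SOC): 0.1724 - 0.0313 = +0.1412, or +14.1 points.
- Fisher, with 6 events in 61. P(5 on Customizable) = C(29,5) × 32 / C(61,6) = 3,800,160 / 55,525,372 = 0.0684. The tables that are no more likely are 6 v 0 (0.0086) and 0 v 6 (0.0163). Two-sided p = 0.0684 + 0.0086 + 0.0163 = 0.093.
- 95% CI, Miettinen-Nurminen: -1.2 to +32.1 points. Newcombe gives -1.8 to +31.6, Wald -0.9 to +29.1 and Agresti-Caffo -2.5 to +29.5.
- A 95.2% interval, matching alpha 0.048, is -1.4 to +32.3 (Miettinen-Nurminen).
- Planned effect: 8.75 - 35 = -26.25 points. It lies far below every lower limit. The p-value of 0.093 alone does not show this.

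**5. CRI precision.** The documents give no CRI counts. As an assumption, take the CRI subjects to be among the interim SSC subjects. Protocol 5.7.2 points that way: "If a SSC requires intervention, the procedure must be documented". That allows 0 to 5 of 29 v 0 to 1 of 32, which is 12 combinations. The difference then runs from -3.1 points (0 v 1) to +17.2 points (5 v 0), and the 95% Miettinen-Nurminen interval is 22.7 to 33.3 points wide. Protocol 3.3.1 lists drainage without requiring an SSC. If CRI can occur outside SSC, this range does not apply and none is claimed.

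**The case against.** Several points on the other side stand.

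- **Disclosure.** The SAP calls itself abbreviated, defines CRI, says openly that it will not be analysed and gives a reason. The FAS sentence in SAP 5.3 repeats protocol 10.2.1 and looks carried over. This is a thin rationale, not concealment.
- **The two endpoints are not on the same footing.** A reader might say that the reason applies equally to both. That goes too far: the covariate-adjusted count model asks far more of the data than an unadjusted Fisher test. The argument rests on the fallback.
- **Selective reporting is not shown.** A reader might infer that CRI was dropped because its by-arm result was known. No passage says CRI was looked at by arm. The protocol planned by-arm SSC rates and AE/SAE totals for the review, and SAP 10 reports SSC only. The review was pre-planned, and the SAP prints an unfavourable SSC result and keeps the test.
- **Information remains.** CRF listings stay (SAP 5.4.1), and SSC components and adverse events are tabulated by arm. None of these is a by-arm CRI summary.
- **The interval is recoverable.** With rates and denominators reported, a reader can compute it. Confidence intervals also survive in the SAP's abbreviations and formatting rules, so the omission may be a drafting slip. But a decimal-place rule plans no interval, and SAP 1 defers to the protocol for objective, design and endpoints, not for analyses.

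**Conclusion.** The point holds in this form. Early termination can justify not fitting the ZIP/ZINB model. It does not justify cancelling all CRI analysis, because the protocol's own fallback covers that case, and the rationale that protocol 10.7 requires is missing. SAP 4.2, 5.1 and 9 also conflict with 5.3. The documents do not support a claim of withheld data, of a by-arm look at CRI, or of motive. What they support is that the decision postdates the by-arm SSC rates, so the appearance of selection should be removed by showing the table.

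The size of the loss for CRI is unknown, and any CRI interval will be wide. For SSC, the interim illustration is +14.1 points (95% CI about -1.2 to +32.1, p = 0.093). It rests on back-calculated counts and is not the final result. The missing interval is the lesser point. The primary test itself is unaffected. This should be fixed before the report is written.

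**What to change.** 1. **SAP 4.2.** Replace the last sentence with text to this effect: *For each arm and overall, the number and percentage of subjects with one or more CRI will be tabulated on the FAS, with the ITT population as support, together with Fisher's exact test (two-sided 0.05) and a 95% CI for the difference in rates, following the fallback in protocol 10.5.2.1. The ZIP/ZINB model is not fitted because too few events are available after early termination. Results are exploratory.* The sponsor should confirm the statement about event numbers against its data, since the documents give no CRI counts. Using incidence also matches how SAP 4.2 defines the endpoint.
2. **SAP 7.1.** Add the 95% CI for the SSC rate difference on FAS and ITT, name the method (for example Miettinen-Nurminen), and note that the test uses alpha 0.048, so test and interval need not agree exactly.
3. **SAP 5.1, 5.3 and 9.** Bring the three into line with the revised 4.2.

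The cost is a few extra tables and short text edits on data already collected, with no change to trial conduct. The drawbacks are a wide CRI interval and a table that will probably describe many of the same subjects as the SSC table.
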